**ClinicalTrials.gov ID: NCT04650282**

**PI: [name], University of Michigan**

**Protocol Date: 12/3/2020**

# **A Phase II Randomized Controlled Double-Blind Clinical Trial of Sphenopalatine Ganglion Block for Headache after Concussion**

## **1. Project Summary**

While advancements have been made in the understanding of practices to optimize recovery from concussion, the current standard of care remains largely based around the management of physical and cognitive activity levels, as well as physical therapy modalities.[1] Despite optimal use of these measures, some patients do not recover from concussion in a timely manner, leading to prolonged symptomatic period and associated medical costs.[2] There is a lack of direct interventions to improve the recovery from concussion, and so there is a need for further research on potential treatments for concussion.

Headache is among the most common symptoms following concussion,[3] but there are no established treatment guidelines for post-traumatic headache.[4] Sphenopalatine ganglion (SPG) blocks have been used for other headache disorders, with previous studies showing benefit in primary headache disorders including migraine[5] and cluster headache.[6] Anecdotal reports have suggested similar benefit from SPG blocks in chronic post-traumatic headache,[7] but there have been no formal studies establishing this benefit, nor has this been studied in the earlier period of recovery after concussion. Given the high frequency of headache after concussion, and potential physiologic similarities between post-traumatic headache and other headache disorders such as migraine, the SPG block has potential as treatment for post-traumatic headache that may improve recovery from concussion.

## **2. Objective**

The objective of this study is to determine if a SPG block performed after concussion is associated with improvements in post-traumatic headache. The primary outcome will be measured by a reduction in headache severity score of 50% or more in the 48 hours following the procedure compared to the 48 hours prior to the procedure. Secondary objectives will be measured by a reduction in Patient Global Impression of Change rating, number of headache occurrences, days with headache, hours per day with headache, and as-needed headache medication uses. Exploratory objectives are to evaluate if a SPG block improves other non-headache concussion symptoms, as measured by Sport Concussion Assessment Tool version 5 (SCAT5) symptom numbers and severity scores at baseline prior to the procedure and following the procedure; and to evaluate if a SPG block results in improvement in physiologic changes related to potential autonomic nervous system dysfunction due to concussion, as measured by comparisons in orthostatic heart rates and resting heart rate variability recorded prior to and after the procedure.

## **3. Specific Aims/Hypothesis:**

Specific Aim #1: To evaluate the effects of a SPG block on headache severity after concussion. We hypothesize that a greater reduction in mean headache severity score in patients who receive a SPG block with lidocaine in the 48 hours after the SPG block compared to the 48 hours before the SPG block. We also hypothesize that patients who receive a SPG block with lidocaine will report lower mean Patient Global Impression of Change (PGIC) scores at two hours and 24 hours post-SPG block compared to those who receive placebo.

## **A Phase II Randomized Controlled Double-Blind Clinical Trial of Sphenopalatine Ganglion Block for Headache after Concussion**

Specific Aim #2: To evaluate the effects of a SPG block on headache frequency and duration after concussion. We hypothesize that patients who receive a SPG block with lidocaine will report less headache days, less headache episodes, and a lower mean number of hours with headache per day than the patients who receive a placebo SPG block in the one week after the SPG block compared to the one week before the SPG block.

Specific Aim #3: To evaluate the effects of a SPG block on as-needed headache treatments after concussion. We hypothesize that patients who receive a SPG block with lidocaine will report a lower mean number of doses of as-needed headache treatments per day than the patients who receive a placebo SPG block in the 48 hours and one week after the SPG block compared to the 48 hours and one week before the SPG block.

Exploratory Aim #1: To evaluate the effects of a SPG block on non-headache concussion symptoms. We hypothesize that patients who receive a SPG block with lidocaine will report lower symptom scores for nausea or vomiting, dizziness, blurred vision, sensitivity to light, and sensitivity to noise than those who receive a placebo SPG block in the 24 hours, 48 hours and one week after the SPG block compared to the 24 hours, 48 hours, and one week before the SPG block.

Exploratory Aim #2: To explore the potential effects of a SPG block on heart rate measurements. We hypothesize those receiving a SPG block with lidocaine will have lower rates of abnormal orthostatic heart rate elevations on standing and higher RMSSD (root-mean square differences of successive R-R intervals) than those who receive a placebo SPG block at 15 minutes following the SPG block compared to before the SPG block.

### **4. Background**

The sphenopalatine ganglion (SPG) is a collection of neurons in the pterygopalatine fossa with parasympathetic, sympathetic, and sensory components that have been implicated in neurologic conditions causing headache and facial pain. Blockade of the SPG has been performed using different methods, including introduction of a local anesthetic (e.g. lidocaine) into the nasal passage using a soft catheter. There is evidence of sustained relief from SPG blockade in primary headache disorders, including chronic migraine and cluster headache. Additionally, there is a case report showing benefit in post-concussion syndrome. However, there have been no studies evaluating the use of SPG blocks for post-traumatic headache in the early symptomatic period after concussion.

Autonomic nervous system dysfunction that has been demonstrated following concussion is believed to play a role in symptom generation. As the SPG is an important relay center for autonomic nervous system transmission, and the benefits of SPG blocks may be related to modulation of autonomic function, it is anticipated that using SPG blocks in symptomatic concussion patients may improve their recovery. The current standard of care in managing sport-related concussion is largely based

## **A Phase II Randomized Controlled Double-Blind Clinical Trial of Sphenopalatine Ganglion Block for Headache after Concussion**

around management of physical and cognitive activity levels, as well as over-the-counter medications for symptom management and physical therapy modalities.[1] However, despite optimal use of these measures, for some patients symptoms of concussions do not resolve in a timely manner, leading to prolonged symptomatic period and associated medical costs.[2] Therefore, this proposed trial has potential to fill the need for additional treatments to optimize recovery from concussion.

### **5. Study Device**

The SpenoCath device is a soft, flexible catheter that is indicated to deliver fluid (such as medication) into the nasal passage, which can facilitate the direction of fluid to the pterygopalatine fossa where the sphenopalatine ganglion resides. The device is a disposable, single use catheter that is attached to a syringe which contains medications (such as local anesthetics) used in procedures such as SPG blocks. The user inserts the device into the nares of the patient and advances a soft, angled tip that directs the medication to the target area within the nasal passage. It is designed to be used by trained medical professionals.

### **6. Methodology**

#### *6.1 Study Sites:*

This is a single-center study that will be completed at the University of Michigan (UM). Subjects will be enrolled from concussion clinics at UM. Research visits will be completed either at the conclusion of a scheduled clinic follow-up visit, or as a separate research visit in the clinic space or an approved research space at UM.

#### *6.2 Study Duration:*

The anticipated enrollment period will be approximately nine months. Enrollment will begin following IRB approval and completion of other necessary regulatory approvals.

#### *6.3 Participants:*

Participants in this study will include patients between 18 and 60 years of age who have been diagnosed with a concussion. Participants will be randomized into one of two groups:

1. Treatment: participants in this group will receive a SPG block using an aqueous 1% lidocaine solution.
2. Control: participants in this group will receive an identical placebo SPG block using a normal saline solution.

#### *6.4 Inclusion criteria:*

Participants will be eligible for this study if they are between the ages of 18 and 60 years of age, have been diagnosed with a concussion by a specialist trained in the care of concussion based on clinical history and physical examination findings consistent with most recent consensus guidelines,[1] are

## **A Phase II Randomized Controlled Double-Blind Clinical Trial of Sphenopalatine Ganglion Block for Headache after Concussion**

greater than 14 days from the date of their injury, and are experiencing  $\geq 4$  occurrences of headache per week lasting at least 1 hour per occurrence, each with a headache severity score  $\geq 2$  out of 6.

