### *6.6 Recruitment:*

Patients between the ages of 18 and 60 years of age with post-traumatic headaches due to concussion will be recruited from concussion clinics at the University of Michigan. Patients will be identified by providers at their clinics if they are eligible for the study, and they will be recruited by an approved study team member.

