## A Phase II Randomized Controlled Double-Blind Clinical Trial of Sphenopalatine Ganglion Block for Headache after Concussion

Potential participants who are eligible for the study will be identified from a concussion clinic at the University of Michigan and will complete the informed consent process. After enrolling in the study, they will be linked to a daily online survey which will ask them to record daily symptom severity scores using the Sport Concussion Assessment Tool version 5 (SCAT5) symptom checklist, rating symptoms (including headache) on a scale of 0 to 6, with 0 corresponding to “absent” and 6 corresponding to “severe.” They will also be asked to record the number of headache episodes, the number of hours with headache, and the number of doses of as-needed headache medication usage every 24 hours for the one week prior to the research visit.

Participants will take part in one in-person research visit, during which the SPG block procedure will be performed. At the beginning of the visit, participant demographic information and baseline characteristics will be recorded, including age, sex, height, weight, date of concussion, history of baseline migraine, depression, anxiety, or ADHD, and history of previous concussions. The participant also will complete the 22-item SCAT5 symptom checklist, as before. Participants will then be fitted with a chest-worn Polar heart rate monitor, which will record resting heart rate and R-R interval while in the supine position. Heart rate will then be recorded immediately after standing, and after standing for two minutes. Next, the SPG block procedure will be performed, as described below. 15 minutes after the procedure, heart rate and R-R interval will be recorded in identical fashion to the pre-procedure recordings. Finally, the participant will again complete the SCAT5 symptom checklist.

Following the research visit, they will record SCAT5 symptom scores, headache episodes, headache hours, and as-needed headache medication usage every 24 hours for the one week following the research visit, identical to the pre-procedure recordings. Additionally, they will complete the SCAT5 symptom checklist and rate their status on the PGIC scale at two hours post-SPG on the day of the research visit. Their direct participation in this study will conclude after the one week post-SPG block survey data is recorded.

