For post-hoc analyses, an independent samples t-test (for normal distributions) or Wilcoxon rank-sum test (for non-normal distributions) will be used to compare mean differences, and chi-square tests (for normal distributions) or McNemar's tests (for non-normal distributions) will be used to compare proportional differences.

Participant characteristics will be reported by treatment group, and these will be evaluated for any differences between groups in any characteristic variables, including age, sex, baseline history of migraine, baseline history of depression or anxiety, baseline history of ADHD, previous history of concussions, and referral for cervical and/or vestibular physical therapy. If any differences in these

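### Time since injury is open-ended beyond 14 days and is recorded, but has no pre-specified place in the randomisation or analysis; it should be a fixed covariate, and the early-period rationale should be reconciled with the open window

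*Combined protocol and SAP*

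**What the plan says.** **Eligibility.** Section 6.4 requires that patients be "greater than 14 days from the date of their injury, and are experiencing" a minimum headache frequency, duration and severity. That is the only rule on timing. The exclusion criteria (6.5) set no upper limit, and neither does recruitment (6.6): "Patients between the ages of 18 and 60 years of age with post-traumatic headaches due to concussion will be recruited from concussion clinics".

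**Rationale.** Section 4 states that "there have been no studies evaluating the use of SPG blocks for post-traumatic headache in the early symptomatic period after concussion". Section 1 makes the same point ("nor has this been studied in the earlier period of recovery after concussion") but first says of longer-standing headache: "Anecdotal reports have suggested similar benefit from SPG blocks in chronic post-traumatic headache", adding that no formal study has established this.

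**Objective.** Section 2 aims "to determine if a SPG block performed after concussion is associated with improvements in post-traumatic headache". It gives no time window, and the aims in section 3 give none either.

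**Data and analysis.** Section 6.10 lists among the items recorded at the research visit "date of concussion, history of baseline migraine, depression, anxiety, or ADHD, and history of previous concussions". Section 6.14 specifies block randomisation and names no stratification factor. The primary ANCOVA in section 8 has two independent variables, the pre-treatment score and the treatment. Section 8 also compares participant characteristics between groups, "including age, sex, baseline history of migraine, baseline history of depression or anxiety, baseline history of ADHD, previous history of concussions" and referral for physical therapy, and adds to the model any that differ. Time since injury is not named there.

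**The concern.** A patient a few weeks after concussion may still be improving spontaneously, while a patient a year or more out may have a stable headache pattern. Sections 1 and 4 recognise that some patients do not recover promptly, so the plan itself accepts that recovery courses differ. Time since injury is then plausibly prognostic for the post-treatment score even at a given pre-treatment score.

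Two things are at stake. The first is precision and chance imbalance. A prognostic variable left out of the model adds residual variance, and in a trial of 24 an uneven split between arms can mimic or mask a block effect. The conditional rule in section 8 is a weak safeguard, because the variable is not named, no criterion for a difference is given, and the model would depend on the data observed. The second is interpretation. The rationale leans on the early period, but nothing in the plan determines how many participants will come from it.

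**Working it through.** **Inputs from the protocol.** N = 24, 12 per group, 80% power, alpha 0.05 (section 6.13). The lower bound is 14 days with no upper bound (6.4). The plan states no effect size, standard deviation, sidedness or expected mix of early and late patients, so its sample size cannot be reproduced. The point does not depend on reproducing it.

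**Assumption.** Half of the participants are chronic. The documents give no figure for this.

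**Step 1: chance imbalance, exactly 12 of 24 chronic.** Let X be the number of chronic patients in one arm of 12. X is hypergeometric, with P(X = k) = C(12,k)² / C(24,12) and C(24,12) = 2,704,156. The gap between arms is |2X − 12| patients, which is always even. A gap of 20 points is 0.20 × 12 = 2.4 patients, so here it takes 4 or more (33 points), that is X ≤ 4 or X ≥ 8.
- P(X = 6) = 924² / 2,704,156 = 853,776 / 2,704,156
- P(X = 5 or 7) = 2 × 792² / 2,704,156 = 1,254,528 / 2,704,156
- P(gap of 20 points or more) = 1 − 2,108,304 / 2,704,156 = **0.22**

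**Step 2: each patient independently chronic with probability 0.5.** The difference in counts, shifted by 12, is Binomial(24, 0.5). A gap of 3 or more patients now qualifies.
- P(gap of 2 or fewer) = [C(24,12) + 2C(24,11) + 2C(24,10)] / 2²⁴ = (2,704,156 + 4,992,288 + 3,922,512) / 16,777,216 = 0.69
- P(gap of 20 points or more) = 1 − 0.69 = **0.31**

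A normal approximation, with standard error √(2 × 0.25/12) = 0.204, gives about 0.33. The exact figures are preferable with counts this small.

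**Step 3: what a gap does to the estimate.** Let δ be the difference in expected post-treatment score between early and chronic patients with the same pre-treatment score. An unadjusted gap of g in chronic share shifts that trial's treatment estimate by g × δ. With 4 of 12 patients, g = 0.33, so each point of δ on the 0–6 scale moves the estimate by 0.33 points. The documents do not give δ, so the size of the distortion cannot be stated.

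**Step 4: could a later split by injury date supply the early-period estimate?** Solving for the effect that gives 80% power with 12 per arm (two-sided t-test, noncentrality d√(n/2)) yields d = 1.20. At that effect, power in early patients alone would be:

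| Share early (assumed) | Early per arm | Power |
|---|---|---|
| 75% | 9 | 66% |
| 50% | 6 | 47% |
| 25% | 3 | 21% |

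A subgroup would be weak unless most participants were early.

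**Step 5: cost of adjusting.** The primary ANCOVA has an intercept, the baseline score and treatment, leaving 24 − 3 = 21 residual degrees of freedom. One further continuous covariate leaves 20.

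**The case against.** A reader might infer that the trial cannot answer its own question because the early period is the gap it sets out to fill. The documents do not support that. The objective and aims set no time window, and section 1 names two gaps: no formal study of chronic post-traumatic headache, and none in the earlier period. An open window is compatible with both, and a mostly early sample would still be informative about the early period. What stands is narrower: the plan does not assure an estimate specific to that period.

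A reader might also infer that spontaneous recovery over two weeks of diary data contaminates the primary result. The primary comparison uses the 48 hours either side of the block and conditions on the pre-treatment score, so drift has less room to act there. The argument fits the one-week outcomes better. Nor is there bias by design, since randomisation balances time since injury on average.

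Two further points deserve weight. The list of characteristics in section 8 is introduced as inclusive, and the date of concussion is recorded with the baseline data, so the wording could stretch to time since injury. That is permission and not a commitment, and adjustment would still wait on an observed difference. An upper limit on time since injury would also trade generalisability and recruitment for homogeneity in a small trial whose size already took recruitment potential into account. That objection is sound, and it is a reason not to make a limit the remedy.

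**Conclusion.** The point holds as an inexpensive improvement to the analysis together with a mismatch of wording to reconcile. A plausibly prognostic variable is recorded, can range widely under section 6.4, and has no pre-specified role. Under the assumed half-and-half mix, an imbalance of 20 points or more would arise in 22% of allocations with the mix fixed, or 31% with independent classification. These figures describe imbalance in a covariate and not error in the treatment effect, which depends on an unstated difference in recovery between early and chronic patients. The effect on the 48-hour primary outcome is probably smaller than on the one-week outcomes. The documents do not support a conclusion of systematic bias, or of a trial that can say nothing about early headache.

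**What to change.** 1. In section 8, pre-specify time since injury, calculated from the recorded date of concussion, as a fixed covariate in the primary ANCOVA and in the one-week ANCOVA models, regardless of any observed imbalance. A log transform is one reasonable form, since the range is unbounded above. The form should be fixed before unblinding.
2. Report time since injury by arm in the baseline table.
3. Reconcile the early-period rationale in sections 1 and 4 with the open window in section 6.4, and confine conclusions to the population actually enrolled. Which window to adopt, if any, is a clinical decision for the sponsor, and no cut-off is proposed here.

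Items 1 and 2 need no new data. They cost a few lines of analysis text and one residual degree of freedom (21 to 20 in the primary model). Item 3 costs only wording if the open window is kept. Narrowing eligibility could slow recruitment.

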### *6.5 Exclusion criteria:*

Patients will be excluded if they have an allergy to local anesthetic of the amide type (e.g. lidocaine), frequent epistaxis (i.e. more than one nose bleed per month), bleeding disorders, are pregnant, are at increased risk for methemoglobinemia (including patients with glucose-6-phosphate dehydrogenase deficiency, congenital or idiopathic methemoglobinemia, cardiac or pulmonary compromise, and concurrent exposure to oxidizing agents or their metabolites and drugs associated with methemoglobinemia), have history of any of the following: nasal or facial fracture, nasal septal defect, any other craniofacial abnormality, hepatic disease, Adam-Stokes syndrome, Wolff-Parkinson-White syndrome, or severe degrees of sinoatrial, atrioventricular, or intraventricular heart block, or if they begin a different headache treatment at the time of study enrollment.

### *6.6 Recruitment:*

Patients between the ages of 18 and 60 years of age with post-traumatic headaches due to concussion will be recruited from concussion clinics at the University of Michigan. Patients will be identified by providers at their clinics if they are eligible for the study, and they will be recruited by an approved study team member.

### *6.7 Informed Consent:*

Eligible patients will be consented in person, over the telephone, or over a video visit after a discussion that includes the risks, benefits, and alternatives to participating in the study. An informed consent document that is approved by the IRB will be used to document consent. The informed consent process will be completed by a trained, approved member of the study team at the clinic visit at which the patient is identified for participation in the study. Patients will be provided a paper copy of the signed informed consent document.

